8.1.3. Visit 3: Month 6 (± 2 weeks) (End of Study/Early Termination)

The following assessments will be performed at Visit 3.

- Concomitant medications
- Vital signs
- Weight measurement
- Urine pregnancy test (for female subjects of childbearing potential only)
- Tympanometry
- Audiometry
- Otoscopy
- C-SSRS assessment, Since Last Visit version
- Meniere's symptom questionnaire
- Adverse events

8.1.4. Unscheduled Visit

The following assessments will be performed at an unscheduled visit.

- Concomitant medications
- Vital signs
- Tympanometry, as indicated
- Audiometry, as indicated
- Otoscopy
- C-SSRS assessment, Since Last Visit version

Adverse events

8.2. Safety Evaluations

Safety assessments include:

- Vital Signs, Height and Weight Measurements
- Tympanometry
- Audiometry
- Otoscopy
- C-SSRS Assessment
- Concomitant Medications
- Adverse events (see Section 9)

8.2.1. Vital Sign, Height and Weight Measurements

Vital sign measurements (including systolic and diastolic blood pressure and pulse rate) will be collected at all study visits. Blood pressure and pulse rate will be measured after subjects have been seated for 5 minutes and while subjects are in a sitting position. Height and weight will be measured at Visit 1 and weight will be measured again at Visit 3.

8.2.2. Urine Pregnancy Test

A urine pregnancy test via dipstick will be conducted only on women of childbearing potential at all study visits. The urine pregnancy test must be conducted and confirmed negative prior to administration of OTO-104 at Study Visits 1 and 2.

8.2.3. Tympanometry

Tympanometry assessments will be used to assess the mobility and compliance of the tympanic membrane, pressure and volume in the middle ear, and function of the tympanic membrane, ossicles and eustachian tube. Tympanograms will be completed in both ears at all study visits. Subjects wearing hearing aids should be instructed not to wear their hearing aids during the tympanometry assessment.

8.2.4. Audiograms

Audiometric assessments will be used to assess hearing function in both ears. Audiograms should be conducted at 500, 1000, 2000, 4000 and 8000 Hz for both air and bone conduction at all study visits. Both air and bone conduction thresholds will be assessed. Pure tone averaging bone and air conduction testing will be done at 500, 1000, and 2000 Hz frequencies. Subjects wearing hearing aids should be instructed not to wear their hearing aids during the audiogram.

Audiometric assessments must be conducted in accordance with American-Speech-Language-Hearing Association Guidelines (ASHA, 2005). Equipment calibration must be current and documented. The audiometric assessments must be conducted by a licensed audiologist or a

qualified assistant with appropriate training under the direct supervision of a licensed audiologist.

8.2.5. Otoscopy

Otoscopic exams will be used to assess the auditory canal, the appearance of the tympanic membrane, and the healing of the intratympanic injection site. Otoscopic examinations will be performed in both ears at all study visits during the study by the physician. Presence and size of tympanic membrane perforations will be recorded. Perforations of the tympanic membrane will be captured as adverse events (AEs) only if the perforation increases in size and does not resolve by the end of the study. Subjects wearing hearing aids should be instructed not to wear their hearing aids during the otoscopic exam.

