9. ADVERSE EVENT (AE) REPORTING

Timely, accurate, and complete reporting and analysis of safety information from clinical trials will be conducted in accordance with Good Clinical Practice.

All AEs, including SAEs reported or observed during or after dosing with the study drug will be recorded on the AE page of the eCRF for all enrolled subjects. Information to be collected includes description of event, date of onset, investigator-specified assessment of the severity and relationship to study drug, date of resolution of the event, seriousness, any required treatment or evaluations, and outcome. Adverse events resulting from concurrent illnesses, reactions to concurrent illnesses, reactions to concurrent medications, or progression of disease states must also be reported. Perforations of the tympanic membrane will be captured as AEs only if the perforation increases in size and does not resolve by the end of the study.

If the existing medical condition worsens at any time after application of study drug, it should be recorded as an AE.

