9.1. Adverse Event Classification Definitions

Adverse Event:

An AE is any unfavorable and unintended diagnosis, symptom, sign, syndrome or disease which occurs during the study, having been absent at baseline, or, if present at baseline, appears to worsen.

This includes any occurrence that is new in onset or aggravated in severity or frequency from the baseline condition, including abnormal results of diagnostic procedures and/or laboratory test abnormalities, which are considered AEs if they:

- result in discontinuation from the study
- require treatment or any other therapeutic intervention
- require further diagnostic evaluation (excluding a repetition of the same procedure to confirm the abnormality)
- are associated with clinical signs or symptoms judged by the investigator to have a significant clinical impact

Serious Adverse Event (SAE):

An SAE is defined as any untoward medical occurrence that:

- results in death,
- is life-threatening (Note: the term "life-threatening" refers to an event in which the subject was at risk of death at the time of the event rather than to an event which hypothetically might have caused death if it were more severe.),
- requires in-patient hospitalization or prolongation of existing hospitalization,
- results in persistent or significant disability/incapacity, or
- is a congenital anomaly/birth defect.

Medical and scientific judgment should be exercised in deciding whether expedited reporting is appropriate in other situations, such as important medical events that may not be immediately life-threatening or result in death or hospitalization but may jeopardize the subject or may require intervention to prevent one of the other outcomes listed in the above definition. These events should be considered serious.

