9.2. Monitoring of Adverse Events

9.2.1. All Adverse Events

All AEs will be analyzed for safety. Those meeting the definition of SAE must be reported using the SAE Form. Subjects should voluntarily report any AEs or report AEs in response to general, non-directed questioning (e.g., "How has your health been since the last visit?"). For each AE volunteered by the subject, the investigator should obtain all the information required to complete the AE page of the eCRF, in accordance with the guidelines that accompany it.

All AEs, regardless of seriousness, severity, or presumed relationship to study therapy, must be recorded using medical terminology in the source document and on the eCRF. Whenever possible, diagnoses should be given when signs and symptoms are due to a common etiology (e.g., cough, runny nose, sneezing, sore throat, and head congestion should be reported as "upper respiratory infection"). Investigators must record on the eCRF their opinion concerning the relationship of the AE to study therapy. All measures required for AE management must be recorded in the source document and reported according to sponsor instructions.

Any non-serious AE that occurs after the dose of study drug must be reported in detail on the appropriate eCRF page and followed until resolution, stabilization, or the End of Study Visit. The description of the AE will include description of event, date of onset, date of resolution, investigator assessment of severity and relationship to study drug, seriousness, any required treatment or evaluations, and outcome.

The sponsor assumes responsibility for appropriate reporting of AEs to the regulatory authorities. The sponsor will also report to the investigators all serious AEs that are unlisted and associated with the use of the drug. The investigators must report these events to the appropriate Institutional Review Board (REC) in accordance with local regulations.

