11.7.1. Adverse Events

Version 18.1 of Medical Dictionary for Regulatory Activities (MedDRA) will be used to code all AEs.

The primary analysis of AEs will consider only treatment emergent AEs (TEAEs), events occurring for the first time, or worsening during or after the first dose of study drug. Subject incidence of TEAEs and SAEs will be tabulated by preferred terms and system organ class. These analyses may also be tabulated by visit, time of onset and/or cumulative exposure. In addition, severity and relationship to study drug will also be presented. Adverse events will be presented by descending order of frequency in MedDRA system organ class and preferred term.

Subgroup analyses of AEs by gender will be examined. Listings of all SAEs, AEs leading to study withdrawal, and deaths on-study will also be included. Duration and outcome of each AE will be reported in subject listings.

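### The tympanic membrane perforation rule in Sections 8.2.5 and 9 conflicts with the general AE rules when a perforation meets an AE trigger, or worsens from baseline, and then closes

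*Combined protocol and SAP*

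**What the plan says.** **Perforation rule.** Section 8.2.5 says perforations are "captured as adverse events (AEs) only if the perforation increases in size and does not resolve by the end of the study". Section 9 repeats it: "Perforations of the tympanic membrane will be captured as AEs only if the perforation increases in size", followed by the same condition of non-resolution at study end. Both conditions must hold. Neither sentence is limited to the injection puncture.

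**General rules.** The next paragraph of Section 9 says: "If the existing medical condition worsens at any time after application of study drug, it should be recorded as an AE". Section 9.1 defines an AE as something unfavorable and not intended, "having been absent at baseline, or, if present at baseline, appears to worsen". It counts an abnormal diagnostic finding as an AE if any one of four triggers is met. Two of these are "result in discontinuation from the study" and "require treatment or any other therapeutic intervention"; the others are further diagnostic evaluation and clinically significant signs or symptoms. Section 9.2.1 adds: "All AEs, regardless of seriousness, severity, or presumed relationship to study therapy, must be recorded using medical terminology in the source document". The same requirement applies to the eCRF.

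**Use of the data.** Section 8.2.5 has the presence and size of perforations recorded, with otoscopy of both ears at all study visits; Section 8.1.4 includes otoscopy at unscheduled visits. Section 11.7.1 bases the primary AE analysis on TEAEs and says: "Listings of all SAEs, AEs leading to study withdrawal, and deaths on-study will also be included". Section 11.7.3 tabulates otoscopic classifications by visit and by ear. Section 14.7 schedules a review of AEs in the ear and labyrinth SOC at least every other month, depending on enrollment rate.

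**The concern.** Safety of repeat intratympanic injection is the trial's only objective (Section 2), and each injection passes a needle through the tympanic membrane (Section 6.1). Perforation is therefore a local harm on which readers will want a clear figure. Under the perforation rule, a perforation that was treated, or that led a subject to withdraw, loses AE status if it has closed by the last visit. Under the general rules it keeps that status, with closure as its outcome. Nothing in the text says which rule governs. If sites follow the perforation rule, the AE tables understate perforations that had clinical consequences.

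**Working it through.** The plan gives no figure to reproduce, so the check sets the rules side by side.

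**Step 1: the role of resolution elsewhere.** Section 9.1.3 records an AE as ongoing or resolved. Section 9.2.1 uses resolution to end follow-up. Section 11.7.1 lists the duration and outcome of each AE. In all three, resolution describes an event that is already an AE. Only the perforation rule makes it a test of AE status.

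**Step 2: the cases.** A trigger means one of the four in Section 9.1.

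| Case | General rules (9, 9.1, 9.2.1) | Perforation rule (8.2.5, 9) | Result |
|---|---|---|---|
| Injection puncture, no trigger, heals normally | Arguably not an AE, since an AE must be unintended | Not an AE | No clear conflict |
| New perforation, trigger met, closed by study end | AE | Not an AE | Conflict, whatever the size reference |
| Perforation present at baseline, enlarges, then closes | AE under the worsening sentence | Not an AE | Conflict |
| New perforation, trigger met, open at study end, no larger than when first seen | AE | AE if compared with a perforation-free baseline; not an AE if compared with the first post-dose exam | Conflict only on the second reading |
| New perforation, trigger met, enlarges, open at study end | AE | AE | None |

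**Step 3: the size reference.** The perforation rule does not say which exam size is compared with. Section 9.1 uses baseline for AEs in general. With a perforation-free baseline, any new perforation is larger than before, so the enlargement condition is met and only closure separates the rules.

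**Step 4: timing.** AE status under the perforation rule can be confirmed only at Month 6 or early termination. A review at least every other month cannot see the event as an AE before then.

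**Step 5: what leaves the AE outputs.** In the conflict cases, the perforation term is absent from the TEAE tables and from the scheduled ear review (assuming it would be coded to that SOC). It is also absent from the listing of AEs leading to withdrawal if it was the recorded cause.

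**Step 6: size.** No perforation rate is given, so the undercount cannot be calculated. At the maximum enrollment of 300, if all are dosed, each subject left out lowers the reported incidence of the term by 1/300 = 0.33 percentage points.

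**The case against.** The strongest defence is that this is a deliberate, specific exception. It uses a word of exclusion, appears twice in matching terms, and in Section 9 sits in the paragraph that requires AEs to be recorded. The procedure necessarily pierces the membrane, and Section 8.2.6 likewise sets AE criteria specific to one assessment. This explains why an ordinary healing puncture is left out, and that part stands. It does not explain why the sentence covers every perforation, including one that was treated or led to withdrawal, or why Sections 9.1 and 9.2.1 make no mention of an exception.

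The defence also limits the impact, and these points stand:

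- Symptoms or diagnoses that accompany a perforation remain reportable in their own right.
- Serious events are defined separately in Section 9.1 and reported within 24 hours (Sections 9.2.2 and 9.3).
- Treatments (Section 7) and withdrawal reasons (Section 10.2.1) are recorded.
- Section 14.7 commits the sponsor to prompt review of all safety information and of discontinuation reasons.
- Exclusions 4 to 6 in Section 4.3 make a perforation at baseline uncommon, though they do not expressly bar every one.
- Section 11 defers analysis detail to the SAP, so a perforation summary may be planned there.

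**Conclusion.** The conflict is real and should be fixed. It is clear for a perforation that meets a Section 9.1 trigger and later closes, and for a baseline perforation that worsens and then closes. For a new perforation that stays open without growing, it depends on an unstated reference exam. The consequence is an understated perforation term in AE outputs, of unknown size. This assumes that sites apply the perforation rule as written.

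A reader might infer more, but the documents do not support it:

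- **That perforation data are lost.** Presence and size are recorded at otoscopy whatever the AE status.
- **That affected subjects vanish from the AE tables.** Only the perforation term is excluded; accompanying symptoms can still appear.
- **That serious perforations go unreported until study end.** They have their own 24-hour route.
- **That every perforation which does not enlarge is in conflict.** With a perforation-free baseline as reference, a new one counts as enlarged.
- **That every healing puncture should be an AE.** Section 9.1 requires the event to be unintended.

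**What to change.** 1. Reconcile Sections 8.2.5 and 9 with Sections 9.1 and 9.2.1, so that a perforation meeting a Section 9.1 trigger is not excluded solely because it later closes. The sponsor should define how the expected, normally healing injection puncture is handled. The same text should settle the worsened baseline perforation.
2. Record closure as the AE outcome, which Section 11.7.1 already lists.
3. Name the reference exam for enlargement: the study baseline otoscopy, including the final visit of 104-201508 where Section 8.1.1 makes it the baseline.
4. Unless the SAP's otoscopy tables already do so, report for the treated ear the subject incidence of any post-dose perforation and its closure, with 95% confidence intervals, using existing otoscopy data including unscheduled visits. Percentages by visit alone do not give subject-level incidence or closure.

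The cost is a few sentences and at most one table, with no new visits or procedures. The downside is a somewhat higher reported AE rate and one more table to review.

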8.2.6. C-SSRS Assessment

The C-SSRS assessment will be administered at all study visits. The Since Last Visit version of the C-SSRS will be used for subjects enrolling from Study 104-201508 while the Baseline version will be used for all subjects enrolling from Study 104-201403. The Since Last Visit version of the C-SSRS will be used at all subsequent visits. Any subject with a positive score on the Baseline version or an appearance of any new suicidal ideation or suicide behavior since the Baseline version (whether administered in this study or Study 104-201508) should be referred to their primary care provider for follow-up.

If a subject has any post-Baseline C-SSRS score of 1-3 for Ideation (i.e., a "yes" answer to Questions 1, 2, or 3) or a "yes" response to the Non-Suicidal Self-Injurious Behavior question) and the score is higher than the Baseline C-SSRS score, then this assessment should be recorded as an adverse event (AE). This information is reported as indicated in Section 9.1. (Possible AE terms: Suicidal plans, Suicidal ideation, Suicidal tendency, Suicidal behavior, Suicidal intention, Suicidal depression, Active suicidal ideation, Passive suicidal ideation, Self-injurious behavior without suicidal intent).

If a subject has any post-Baseline C-SSRS score of 4 or 5 for Ideation (i.e., a "yes" answer to question 4 or 5) and/or any questions answered yes for Suicidal Behavior (with the exception of a "yes" response to the Non-Suicidal Self-Injurious Behavior question), and this was not observed at Baseline, then this assessment should be recorded as a serious adverse event (SAE). This information is reported as indicated in Section 9.2.2.

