8. STUDY EVALUATIONS

8.1. Study Procedures by Visit

8.1.1. Visit 1: Day 1 (Screening/Baseline/Dose No. 1)

The following assessments will be performed at Visit 1. For subjects enrolling directly (within 1 month) from Study 104-201508, the tympanometry, audiometry, otoscopy and C-SSRS assessment data collected at the final visit of Study 104-201508 will serve as the Baseline data for Visit 1.

The following assessments will be performed at Visit 1.

- Informed consent
- · Confirm eligibility criteria
- Medical history
- Concomitant medications
- Vital signs
- Height and weight measurements
- Urine pregnancy test (for female subjects of childbearing potential only)
- Tympanometry
- Audiometry
- Otoscopy
- C-SSRS assessment: Baseline version or Since Last Visit version
- Meniere's symptom questionnaire
- Administer OTO-104 (all assessments in the above list must be conducted prior to OTO-104 administration)
- Adverse events (to be collected during or after OTO-104 administration)

8.1.2. Visit 2: Month 3 (± 2 weeks) (Follow Up and Dose No. 2)

The following assessments will be performed at Visit 2.

- Concomitant medications
- Vital signs
- Urine pregnancy test (for female subjects of childbearing potential only)
- Audiometry
- Tympanometry
- Otoscopy
- C-SSRS assessment, Since Last Visit version
- Meniere's symptom questionnaire
- Administer OTO-104 (all assessments in the above list must be conducted prior to OTO-104 administration)
- Adverse events (to be collected during or after OTO-104 administration)

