11.7.7.1. C-SSRS: Baseline Version

The C-SSRS assessment will be administered at all study visits. The Since Last Visit version of the C-SSRS will be used for subjects enrolling directly (within 1 month) from Study 104-201508 while the Baseline version will be used for all other subjects. The Since Last Visit version of the C-SSRS will be used at all subsequent visits. The Baseline version of the scale captures both suicide ideation and suicide behavior (lifetime). There are 5 suicidal ideation questions, each captured as yes/no for the subject's lifetime. Additionally, a sixth suicidal ideation variable will be created to indicate if there was any ideation, regardless of type. There are 4 suicidal behavior questions, each captured as yes/no for the subject's lifetime. A fifth suicidal behavior variable will be created to capture if there was any suicidal behavior regardless of type. An additional question asks if suicidal behavior is present during the visit. All suicidal ideation and behavioral variables as outlined here will be tabulated overall and by treatment group. All C-SSRS data will be included in data listings. There is no inclusion or exclusion criterion associated with the Baseline C-SSRS score.

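### Where Baseline is the lifetime C-SSRS, the Section 8.2.6 AE and SAE triggers do not fire for on-study ideation or behavior already in the lifetime record, in conflict with Section 9.1

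*Combined protocol and SAP*

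**What the plan says.** Section 8.2.6 holds two rules that turn a C-SSRS answer into a safety report. For ideation of 1 to 3, or non-suicidal self-injury, the condition is "and the score is higher than the Baseline C-SSRS score, then this assessment should be recorded as an adverse event (AE". For ideation of 4 or 5, or any suicidal behavior, it is "and this was not observed at Baseline, then this assessment should be recorded as a serious adverse event (SAE".

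Section 11.7.7.1 defines what the Baseline form measures: "The Baseline version of the scale captures both suicide ideation and suicide behavior (lifetime". On the items it says "There are 5 suicidal ideation questions, each captured as yes/no for the subject's lifetime" and "There are 4 suicidal behavior questions, each captured as yes/no for the subject's lifetime". It also says that no entry criterion depends on the Baseline C-SSRS result.

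Which form is used at Visit 1 depends on the parent study. Section 8.2.6 says "The Since Last Visit version of the C-SSRS will be used for subjects enrolling from Study 104-201508 while the Baseline version" goes to those from 104-201403. For subjects entering within 1 month of 104-201508, Section 8.1.1 says that "C-SSRS assessment data collected at the final visit of Study 104-201508 will serve as the Baseline data for Visit 1".

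Section 9.1 defines an AE without reference to the C-SSRS, as something unfavorable "which occurs during the study, having been absent at baseline, or, if present at baseline, appears to worsen".

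**The concern.** The on-study form asks about the period since the last visit. The Baseline form asks about a whole life. A rule that asks whether the first exceeds the second does not test whether anything changed after dosing. It tests whether the subject has ever been at least this unwell before. An event absent at Visit 1 and present at Month 3 can therefore fail both triggers because something similar happened many years ago.

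Safety is the study's only objective. Section 9.2.1 collects AEs by voluntary report or general, non-directed questioning, so the C-SSRS is the one directed question about suicidality. If its triggers do not fire, entry as an AE or SAE, and the 24-hour report under Sections 9.2.2 and 9.3, rest on the investigator applying the general definitions unprompted. The incidence of suicidality AEs and SAEs could then be understated.

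**Working it through.** The plan gives no figure to reproduce on this point; Section 11.1 says the sample size has no power basis. The check runs the two rules through every combination of history and on-study answer.

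**1. Which Baseline applies**
- Subjects from 104-201403: Sections 8.2.6 and 11.7.7.1 and the notes to Table 1 all give the Baseline version at Visit 1. The comparator is lifetime.
- Subjects entering within 1 month of 104-201508: Section 8.1.1 takes the parent study's final-visit C-SSRS as Baseline, and Section 8.2.6 gives the Since Last Visit form at Visit 1. On that reading the comparator is not lifetime. Yet the referral sentence in Section 8.2.6 takes as its reference the Baseline version, including one given in 104-201508.
- Subjects entering later from 104-201508: Section 8.2.6 gives the Since Last Visit form to everyone from that study. Section 11.7.7.1 reserves it for direct entrants and gives all others the Baseline version.

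**2. Ideation, with a lifetime comparator**

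Let b be the lifetime worst level (0 to 5) and s the on-study level (1 to 5), each being the highest item answered yes. The AE rule fires if s is 1 to 3 and s > b. The SAE rule fires if s is 4 or 5 and was not observed at Baseline. Reading *observed* as the same item, and taking a lifetime 5 to include item 4, gives:

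| b | s = 1 | s = 2 | s = 3 | s = 4 | s = 5 |
|---|---|---|---|---|---|
| 0 | AE | AE | AE | SAE | SAE |
| 1 | none | AE | AE | SAE | SAE |
| 2 | none | none | AE | SAE | SAE |
| 3 | none | none | none | SAE | SAE |
| 4 | none | none | none | none | SAE |
| 5 | none | none | none | none | none |

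A positive history (b = 1 to 5) has 5 × 5 = 25 cells. No trigger fires in 1 + 2 + 3 + 4 + 5 = 15; one fires in 25 − 15 = 10. If *observed* instead means any earlier ideation of 4 or 5, the cell b = 4, s = 5 also fires nothing: 16 without a trigger and 9 with one.

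**3. Suicidal behavior, with a lifetime comparator**

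Four yes/no items give 2⁴ − 1 = 15 positive histories. Each is paired with one on-study behavior type: 15 × 4 = 60 combinations. A given type appears in 2³ = 8 histories, so the same item was already recorded in 4 × 8 = 32, and the SAE rule does not fire there. It fires in 60 − 32 = 28. If any past behavior counts as observed, it fires in none of the 60. With an ideation-only history, on-study behavior always fires it.

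**4. One subject, both sections**

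A 104-201403 subject had an aborted attempt and level 5 ideation years ago, has neither at Visit 1, and reports an aborted attempt and level 4 ideation at Month 3.
- Section 8.2.6, SAE rule: both findings are in the lifetime record, so the condition fails.
- Section 8.2.6, AE rule: the score is 4, outside the 1 to 3 range, and is not above 5. It fails too.
- Section 9.1: the event arose during the study and was absent at baseline, so it is an AE.

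A smaller gap: non-suicidal self-injury is a yes/no question, so a score higher than Baseline is undefined for it.

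**The case against.** The best reply is that Section 8.2.6 states when an assessment should be recorded and does not say that nothing else may be. The protocol writes exclusions explicitly where it wants them, as with tympanic membrane perforations in Section 8.2.5. Sections 9, 9.1 and 9.2.1 therefore still require every AE to be recorded. The important-medical-event paragraph of Section 9.1 allows an event that may jeopardize the subject to be treated as serious, and Section 9.3 then requires a report within 24 hours. Section 11.7.7.2 tabulates and lists every Since Last Visit answer, and Section 14.7 lets sponsor and CRO medical staff see safety data as entered.

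This stands, and it rules out several stronger conclusions that a reader might infer:
- That these events are never recorded as AEs or SAEs. The general definitions still reach them.
- That any past history disables the triggers. Ideation above the lifetime worst fires in 10 of 25 cells (9 on the second reading), and behavior after an ideation-only history always fires.
- That every subject is exposed. A lifetime comparator is not established for 104-201508 subjects.
- That the C-SSRS tables are biased. They do not depend on the triggers.
- That a head count can be given. An assumed 5% to 20% with some positive lifetime item would give 300 × 0.05 = 15 to 300 × 0.20 = 60. But the documents support no prevalence, do not say how many subjects come from 104-201403, and do not make every positive item a masking one.

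The reply does not remove the gap. The general route depends on investigator judgment, while Section 8.2.6 is the specific instruction a site has in hand when it scores the form. The reviews named in Section 14.7 cover ear and labyrinth AEs, SAEs and reasons for discontinuation; a C-SSRS answer not raised to an SAE has no scheduled review there.

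**Conclusion.** The point holds for subjects whose Baseline is the lifetime C-SSRS: certainly those from 104-201403, and possibly some or all from 104-201508 until the sections are reconciled. For them, on-study ideation at or below the lifetime worst, or a behavior already in the lifetime record, fires neither trigger, even when it was absent at first dosing. Section 9.1 would count the same event as an AE and might make it serious. The two sections conflict, and directed AE/SAE capture and 24-hour reporting can be missed, although the answers still appear in the C-SSRS tables and listings.

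The extent is 15 or 16 of 25 ideation combinations and 32 or 60 of 60 behavior combinations, depending on how *observed* is read. These count rule outcomes with equal weight and are not event probabilities. The number of subjects affected cannot be derived from the documents.

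**What to change.** In Section 8.2.6, replace the lifetime comparator with the subject's status at first dosing in this study. Suicidal behavior occurring after the first OTO-104 dose, and ideation that is new or worse than at Visit 1, would go to the existing AE or SAE branch whatever the lifetime answers were. A comparator for ideation has to stay: without one, unchanged ideation already present at Visit 1 would become an AE or SAE, contrary to Section 9.1.

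Keep the lifetime answer as a history flag in the listings, so that first and recurrent events can be separated. State which Baseline applies to 104-201508 subjects, reconciling Sections 8.1.1, 8.2.6 and 11.7.7.1. State that Section 9.1 applies to recurrences.

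The cost is a few sentences in Section 8.2.6 and the eCRF guidance. As Section 11.7.7.1 describes the Baseline form, its ideation answers are lifetime only, so ideation status at Visit 1 would need its own entry for subjects given that form. Expect a few more AE and SAE reports and a slightly less favorable suicidality count.
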